6.9.7 Adverse event of special interest

6.9.7.1 Genitourinary infections

Events representing genitourinary infection (e.g. cystitis, urethritis, pyelonephritis, balanitis, vulvovaginitis should be carefully evaluated and documentation of signs, symptoms, infectious agent (bacterial or fungal), and treatment should be undertaken.

6.9.7.2 Renal and urinary disorders

Events that may be related to the diuretic effect of an SGLT2 inhibitor (e.g. nocturia, pollakiuria, polyuria, and dysuria) should be carefully evaluated and documented.

6.9.7.3 Major Adverse Cardiovascular Event (MACE)

Evaluation of major adverse cardiovascular events will be undertaken across the development program for EGT0001442. All events that potentially represent myocardial infarction, cerebrovascular accident (stroke), acute coronary syndrome, or cardiovascular death are to be evaluated by an adjudication committee.

6.9.7.4 Hypoglycemia

Severe hypoglycemia is defined as hypoglycemia with documented blood glucose 2.8 mmol/L (50 mg/dL) or symptoms that promptly resolve with oral carbohydrate, intravenous glucose, or glucagon that require the assistance of medical or paramedical personnel.

6.10 Concomitant Medication Assessments

A concomitant medication is any medication the patient enters the trial using and is expected to continue using for some portion of the trial as well as any medication the patient uses during the course of the trial. All concomitant medications recorded at trial entry must have a related concomitant illness listed under the medical history as ongoing at the time of patient entry into the trial unless the medication is an allowed treatment for the disease under study.

EGT0001442 or placebo are the study drugs and are not considered concomitant medications. The rescue medications for controlling hyperglycemia must be recorded as concomitant medications.

All prescription and over-the-counter medications patients receive pre-study and continue during the trial as well as any new medications started during the trial must be documented on the CRF. This documentation should continue until one week from the end of the last treatment

Concomitant medications will be coded using the World Health Organization dictionary (WHODRUG). A table of concomitant medications based on the anatomic therapeutic chemical classification (ATC) and preferred name will be produced. A listing of concomitant medications will include all medications taken during the course of the study.

Any medications taken prior to the start of the study medication will be listed and summarized.

6.11 Removal of Patients from the Trial or Study Drug

The investigator may withdraw a patient from any of the following reasons:

- A protocol violation occurs,
- A serious or intolerable adverse event occurs,
- A clinically significant change in a laboratory parameter occurs,
- The sponsor or investigator terminates the study, or
- The patient requests to be discontinued from the study.

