9.3 Analysis Populations

This study will be conducted at multiple investigative sites and will likely involve variable numbers of subjects at each site. Enrollment will be on a competitive basis but will be capped at 90 subjects in one center.

All patients in the Intent-to-Treatment (ITT) sample will be analyzed according to the treatment they were randomized to receive, and not according to what they actually received, if different. All efficacy analyses will be performed on the ITT sample. All patients in the Per Protocol (PP) sample will be analyzed according to the treatment actually received, and not according to the treatment they were randomized to receive, in the event there is a discrepancy. The analyses of primary efficacy endpoint and selected secondary efficacy endpoints will be performed on the PP sample. The Safety sample will include all randomized patients who have received study drug. The safety sample will be used for safety analysis.

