10.8 Protocol Violations/Deviations

Protocol "violations" include deviations from the inclusion and exclusion criteria, concomitant medication restrictions, and any other protocol requirement that results in a significant added risk to the patient or has an impact on the quality of the data collected or the outcome of the study. Protocol violations must be reported to the Ethics Committee or Institutional Review Board in a timely manner. Protocol violations must be reported in the final study report.

A protocol deviation occurs when there is non-adherence to study procedures or schedules, as specified by the protocol, which does not involve inclusion/exclusion criteria or the primary endpoint and which does not place the patient at any added risk or affect the data quality or study outcome. If deviations occur, such as a missed visit or missed sampling window, the investigator must decide whether to proceed, for example, whether or not to complete the visit or sample collection outside of the protocol-defined window. The sponsor's medical monitor must be notified immediately when protocol deviations are discovered so that a decision can be made about the continued participation of the subject in the study.

A departure from the protocol for an individual subject can only be made without the Sponsor approval in the event of an emergency. The nature and reasons for the protocol deviation will be recorded in the CRF and the Principal Investigator must notify the Sponsor.

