# Table 14.1-1.1.1 Subject Disposition for Run-in Failures (All Enrolled Subjects)

	Total (N=xxx)
All Enrolled Subjects	xxx
All Randomized Subjects	xxx (xx.x%)
Discontinued Prior to Randomization (Run-in Failures)	xxx (xx.x%)
Reasons Discontinued Prior to Randomization	xxx (xx.x%)
Withdrew Consent	xxx (xx.x%)
Failed Inclusion/Exclusion Criteria	xxx (xx.x%)
Other	xxx (xx.x%)
XXXXXXXXXXXXXXXX	xxx (xx.x%)

Note: Percentages are calculated using the number of subjects enrolled as the denominator.

Source Data: Listing 16.2-2.1

Table 14.1-1.1.2

Subject Disposition for Randomized Subjects

(All Randomized Subjects)

	EGT0001442	Placebo	Total
	(N=xxx)	(N=xxx)	(N=xxx)
Safety Analysis Set	xxx (xx.x%)	xxx (xx.x%)	xxx (xx.x%)
Full Analysis Set	xxx (xx.x%)	xxx (xx.x%)	xxx (xx.x%)
Per Protocol Analysis Set	xxx (xx.x%)	xxx (xx.x%)	xxx (xx.x%)
Completed Active Treatment through Week 24	xxx (xx.x%)	xxx (xx.x%)	xxx (xx.x%)
Discontuned Study before Week 24	xxx (xx.x%)	xxx (xx.x%)	xxx (xx.x%)
Reason for Discontinuing Study before Week 24			
Clinically Significant Change in a Laboratory	xxx (xx.x%)	xxx (xx.x%)	xxx (xx.x%)
Investigator Terminates the Study	xxx (xx.x%)	xxx (xx.x%)	xxx (xx.x%)
Patient Request to be Discontinued from the Study	xxx (xx.x%)	xxx (xx.x%)	xxx (xx.x%)
Protocol Violation	xxx (xx.x%)	xxx (xx.x%)	xxx (xx.x%)
Serious or Intolerable Adverse Event	xxx (xx.x%)	xxx (xx.x%)	xxx (xx.x%)
Sponsor Termiantes the Study	xxx (xx.x%)	xxx (xx.x%)	xxx (xx.x%)
Other	xxx (xx.x%)	xxx (xx.x%)	xxx (xx.x%)
XXXXXXXXXXXXXXXX	xxx (xx.x%)	xxx (xx.x%)	xxx (xx.x%)
XXXXXXXXXXXXXXXX	xxx (xx.x%)	xxx (xx.x%)	xxx (xx.x%)

Note: Percentages are calculated using the number of subjects randomized as the denominator.

Source Data: Listing 16.2-1.1

Table 14.1-1.1.2

Subject Disposition for Randomized Subjects

(All Randomized Subjects)

	EGT0001442 (N=xxx)	Placebo (N=xxx)	Total (N=xxx)
Completed Study	xxx (xx.x%)	xxx (xx.x%)	xxx (xx.x%)
Discontinued Study Early	xxx (xx.x%)	xxx (xx.x%)	xxx (xx.x%)
Reason for Discontinuing Study Early			
Clinically Significant Change in a Laboratory	xxx (xx.x%)	xxx (xx.x%)	xxx (xx.x%)
Investigator Terminates the Study	xxx (xx.x%)	xxx (xx.x%)	xxx (xx.x%)
Patient Request to be Discontinued from the Study	xxx (xx.x%)	xxx (xx.x%)	xxx (xx.x%)
Protocol Violation	xxx (xx.x%)	xxx (xx.x%)	xxx (xx.x%)
Serious or Intolerable Adverse Event	xxx (xx.x%)	xxx (xx.x%)	xxx (xx.x%)
Sponsor Termiantes the Study	xxx (xx.x%)	xxx (xx.x%)	xxx (xx.x%)

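### Protocol 6.11 and 10.8 let a protocol violation or deviation end follow-up without separating stopping study drug from leaving the study, so an obtainable Week 24 HbA1c can be lost

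*Protocol*

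**What the plan says.** **Grounds for removal.** The heading of Protocol 6.11 covers both the trial and the study drug, and the text does not say which of the two a ground applies to. It reads "The investigator may withdraw a patient from any of the following reasons", and the first reason listed is "A protocol violation occurs".

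**Scope of violations and deviations.** Under Protocol 10.8, violations "include deviations from the inclusion and exclusion criteria, concomitant medication restrictions, and any other protocol requirement" with a material effect on patient risk, data quality or outcome. Deviations are the remainder: departures that add no risk and do not affect data quality or study outcome. For these, "If deviations occur, such as a missed visit or missed sampling window, the investigator must decide whether to proceed". The section then says: "The sponsor's medical monitor must be notified immediately when protocol deviations are discovered so that a decision can be made about the continued participation".

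**After removal.** Protocol 7.4 covers subjects removed for drug-related toxicity and subjects who withdraw consent. Protocol Appendix 1 has an early-termination column that includes HbA1c, and SAP Table 1 has one visit a week after the last dose. Nothing schedules a Week 24 HbA1c for a subject removed for a violation or deviation.

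**Analysis.** Protocol 9.3 says "All efficacy analyses will be performed on the ITT sample", and Protocol 9.1.1 says that missing data are not imputed. SAP 7.1 uses the full analysis set with LOCF. SAP 4.3 excludes major deviators from the per protocol set only. The SAP disposition shell (Table 14.1-1.1.2) has a row for "Protocol Violation" among the reasons for discontinuing before Week 24.

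**The concern.** A subject who misses a visit or breaches a concomitant-medication rule can usually still give a Week 24 HbA1c. Ending participation discards that value by choice. The analysis does not need this, because the per protocol set already deals with major deviators.

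The missingness may also be selective. Violations and deviations happen after randomisation, and the decision rests on judgement with no stated criteria. HbA1c is masked after dosing starts (Protocol 5.5), but investigators review self-monitored and fasting glucose at every visit (Protocol 3.1). Those readings are related both to outcome and to treatment. SAP 5.3.1 calls LOCF conservative on the assumption that discontinuation is equal between arms and random. Removal for conduct puts that assumption under avoidable strain.

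**Working it through.** **Inputs.** Effect 0.4, SD 1.0, two-sided alpha 0.05, 150 enrolled per arm, placebo change about zero (Protocol 9.2, SAP 3.5). Evaluable number per arm for about 90% power: 131 (Protocol) or 133 (SAP). No removal rate and no carried-forward effect is given, so both are assumed below.

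**The plan's own figure.** n per arm = 2 × (1.960 + 1.282)² × 1.0² / 0.4² = 131.4, so 132. With power = Φ(d√(n/2) − 1.96), where d is effect/SD:

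- n = 131: 89.9%
- n = 133: 90.4%
- n = 150: 0.4 × √75 − 1.96 = 1.504, so 93.4%

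Both stated sizes reproduce. The noncentral t gives values 0.1 to 0.2 points lower at these sizes. The implied loss allowance is 1 − 131/150 = 12.7% or 1 − 133/150 = 11.3%, and both documents attribute it to loss to follow-up only.

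**Under the SAP rule (LOCF).** The subject stays in the analysis, so n is kept and the effect is diluted. If a fraction f is removed and carries forward a share q of the effect, the effect becomes 0.4 × (1 − f + fq). Placebo change is taken as zero and SD as unchanged.

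| Removed f | Share q | Effect | Power, 150 per arm |
|---|---|---|---|
| 0% | – | 0.40 | 93.4% |
| 5% | 0.5 | 0.39 | 92.2% |
| 10% | 0.5 | 0.38 | 90.8% |
| 5% | 0 | 0.38 | 90.8% |
| 10% | 0 | 0.36 | 87.7% |
| 10% | 0.75 | 0.39 | 92.2% |

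Power reaches 90% when the effect is (1.960 + 1.282)/√75 = 0.374. With q = 0.5 that is f = 2 × (1 − 0.374/0.4) = 13%.

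**Under the protocol rule (deletion).** The effect is kept and n falls.

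| Loss at Week 24 | n per arm | Power |
|---|---|---|
| 5% | 142 | 92.1% |
| 10% | 135 | 90.8% |
| 15% | 127 | 89.0% |
| 11.3%, plus 5% of 150 removed | 125 | 88.5% |

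Only under this rule do removals spend the loss allowance.

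**Selective removal.** The documents give no basis for its size or direction, so no bias figure is offered. Each 1% removed is 3 of the 300 subjects.

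**The case against.** Much of the case on the other side stands, and it rules out several stronger readings.

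- **A reader might infer that a violation or missed visit leads to removal.** It does not follow. Section 6.11 is permissive, and 10.8 calls for a decision, first asking whether to complete the visit or sample outside the window. That discretion has no criteria, which is why the wording matters, but it is not mandatory exit.
- **A reader might infer a contradiction with intention-to-treat.** Protocol 9.3 says how subjects are assigned for analysis, not who may be withdrawn. Under SAP LOCF a removed subject with a baseline and one post-baseline HbA1c stays in the full analysis set. Only a subject removed before any post-baseline HbA1c drops out.
- **A reader might infer that removal always leaves Week 24 empty.** SAP 5.4.2 slots early-withdrawal records by study day, and the Week 24 slot runs from day 149 to 211. A late end-of-treatment HbA1c can fill it. The gap concerns earlier removals.
- **A reader might infer that removals both dilute the effect and use up the loss allowance.** These belong to different missing-data rules and cannot be added together.
- **Continued follow-up would not change the primary result for subjects who stop drug**, because SAP 5.3.1 carries forward on-treatment values. This is correct. The gain in the primary analysis is confined to subjects who stay on drug.
- **Uneven removal would show in the disposition table.** It would, but only after the values were lost.
- **Version.** The protocol supplied is the original of 02 February 2011, and the SAP cites later versions. The SAP row shows that the discontinuation reason persisted. It does not show that 6.11, 7.4 and 10.8 were unchanged, so the current text should be checked.

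**Conclusion.** The point holds as a weakness in the retention wording. The plan lets a violation or deviation end participation, does not separate that from stopping drug, and makes no provision for a Week 24 HbA1c afterwards. An obtainable value is then carried forward from an earlier visit or deleted, depending on which of two conflicting missing-data rules applies.

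The power cost is modest: about 1 to 3 points for 5% to 10% removed with half the effect carried forward. It takes power below 90% only under harsher assumptions, such as 10% removed with none of the effect carried forward (87.7%). A claim that the trial is underpowered for this reason is not supported. The case for change rests on missing data that are avoidable, may be selective, and weaken the assumption behind LOCF. It merits a wording change and does not call for redesign.

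**What to change.** 1. Split Protocol 6.11 into discontinuation of study drug, with grounds left as the sponsor sets them, and withdrawal from the study. State that a protocol violation or deviation alone does not end visits or data collection.
2. Limit the participation decision in 10.8 in the same way.
3. State in 7.4 and Appendix 1 that every randomised subject who has not withdrawn consent keeps the scheduled visits and HbA1c draws through Week 24, whether or not study drug continues.
4. Reconcile Protocol 9.1.1 (no imputation) with SAP 5.3.1 and 7.1 (LOCF).
5. In the SAP, let on-drug Week 24 values from these subjects enter the primary analysis as observed, with post-rescue values still handled under SAP 5.3.2. Flag off-drug values and use them in a supportive analysis of all observed Week 24 values.

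The cost is a wording amendment, visits that are already scheduled for some subjects, and one added supportive analysis. The primary estimate does not change for subjects whose drug is stopped.

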6.12 Other Study Procedures

Approximately 0.5 mL plasma sample will be collected and stored at -20°C at each clinic visit during the treatment period. The samples will be shipped to the analytical laboratory in batches. EGT0001442 plasma concentration may be determined from all or a portion of the samples to verify the drug exposure.

7 STUDY ACTIVITIES

The study activities in each clinic visit are listed below and are presented in Appendix A. Screening period may last up to 21 days (Visit 1 to Visit 2), Run-in period is to be 14 ± 3 days (Visit 2 to Visit 3), Visit 3 to Visit 4 window is 14 ± 3 days. All other visit windows are the nominal duration from randomization ± 7 days.

7.1.1 Visit 1 - Screening (weeks –5 to -2)

The screening can be performed up to 3 weeks from the start of study activities. During the screening period, the following information will be gathered or the indicated procedure will be performed:

- Informed Consent and medical history obtained, and Inclusion/Exclusion criteria evaluated
- Complete physical examination including height and weight
- Vital Signs: blood pressure, pulse, temperature, respiratory rate taken in the sitting position after at least 5 minutes of rest. Blood pressure must be measured twice with at least 3 min apart
- 12 lead ECG taken in the supine position after at least 5 minutes of rest
- Blood draw for hematology (CBC with platelets, WBC with differential), serum chemistry including FPG, and coagulation as detailed in section 6.7.1
- Urinalysis
- Urine screen for drugs of abuse. Drug screening includes amphetamines, barbiturates, cocaine metabolites, opiates, benzodiazepines, and cannabinoids.
- Urine pregnancy test (only for females who are not postmenopausal)
- The subject must be queried to assess compliance with a minimum of a 10 h fast prior to blood draw to ensure the FPG values can be accurately determined. If a subject has not fasted for 10 h, the subject should return within a week after proper fasting.

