After the run-in period, approximately 300 subjects will complete the baseline assessment on day 1 after overnight fasting to confirm their eligibility. The subjects that remain eligible will be randomly assigned to one of the 2 treatment groups on day 1. Randomization will be stratified by study center and based on screening HbA1c (\geq 7 to <8.5% or \geq 8.5 to 10%). The planned doses are 30 mg/day of EGT0001442 or placebo. Each subject will be provided with study drug for 6 weeks, dosing instructions and log, diet and exercise counseling, and a diary card for recording food and fasting glucose information on the days prior to each clinic visit.

Each subject will be instructed to return to the clinic on weeks 2, 6, 12, 18, and 24 for safety monitoring and efficacy assessment including review of adverse events, concomitant medication, ECG, vital signs, physical examinations, testing of blood chemistry and hematology laboratory parameters, and a urinalysis.

Subjects who complete the 24-week treatment period will continue receiving the study drug for an additional 72 weeks. Subjects who receive rescue medication due to poor glycemic

control will continue to receive approved anti-diabetic medications and standard of care per investigator decision according to current treatment guidelines for 72 weeks. In the treatment extension period, subjects must return to the clinic on weeks 36, 48, 60, 72, 84, and 96 for continuous safety monitoring and efficacy assessment, including review of HbA1c values, adverse events, concomitant medication, ECG, vital signs, and physical examinations. A follow up exit visit will be conducted at 1 week after the last dose. Subjects will be advised to see their primary physician and resume standard of treatment to control diabetes.

GLYCEMIC CONTROL

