7.2 Primary Efficacy Phase

7.2.1 Visit 3 – procedures (Day 1 in Week 0)

- The subject must be queried to assess compliance with a minimum of a 10 h fast prior to blood draw to ensure the FPG values can be accurately determined. Only water is permitted. If a subject has not fasted for 10 h, the subject should return within a week after proper fasting.
- Confirm eligibility
- Diary and SMBG review
- Adverse events and pre-treatment medications assessment
- Randomization
- Vital Signs: blood pressure, pulse, temperature, respiratory rate taken in the sitting position after at least 5 minutes of rest. Blood pressure must be measured twice with at least 3 min apart
- 12 lead ECG taken in the supine position after at least 5 minutes of rest
- Dispense study medication based on randomization assignment
- Blood draw for hematology (CBC with platelets, WBC with differential), serum chemistry including FPG, and coagulation as detailed in section 6.7.1
- Urinalysis

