Appendix 1 Schedule of Events

Visit Number		Screening & Run-in		Primary Efficacy Phase						Extension Phase						
		2	3	4	5	6	7	8	9	10	11	12	13	14	ET	
Time Relative to Randomization Visit (weeks) ¹	-5	-2	0	2	6	12	18	24	36	48	60	72	84	96		
Informed Consent	X															
Screening for I/E criteria	X	X	X													
Medical History	X															
Diet & exercise counseling		X				X		X		X		X				
Diary Review			X	X	X	X	X	X	X	X	X	X	X	X	X	
Discontinue anti-diabetic medication		X														
Randomization			X													
Physical exam	X					X		X		X		X		X	X	
Vital signs	X	X	X	X	X	X	X	X	X	X	X	X	X	X	X	
ECG	X		X					X			X			X	X	
Dispense study medication		X	X		X	X	X	X	X	X	X	X	X			
Blood draw for clinical lab test ²			X	X	X	X	X	X	X	X	X	X	X	X	X	
PK sample				X	X	X	X	X	X	X	X	X	X	X		
Urinalysis ³	X		X	X	X	X	X	X	X	X	X	X	X	X	X	
AE^4			X	X	X	X	X	X	X	X	X	X	X	X	X	
Con Med			X	X	X	X	X	X	X	X	X	X	X	X	X	

Confidential Page 57 of 61

EGT0001442 tablet

Clinical Trial Protocol: THR-1442-C-418

02 February 2011

Screening period may last up to 21 days (V1 to V2), Run-in period is to be 14±3 days (V2 to V3), V3 to V4 window is 14±3 days, all other visit windows are the nominal duration from randomization ± 7 days.

Blood sample for these lab tests at the designated visit:

V1: CBC, electrolytes, BUN, creatinine, Lipids (TG, TC, HDL-C), ALT, AST, bilirubin (total and direct), PT, HbA1c, FPG, TSH, aPTT, Hepatitis Screen (HBsAg, HBcAg, HCV)

V3: CBC, electrolytes, BUN, creatinine, Lipids (TG, TC, HDL-c), ALT, AST, bilirubin (total and direct), HbA1c, FPG

V4: CBC, electrolytes, BUN, creatinine, HbA1c, FPG

V5: CBC, electrolytes, BUN, creatinine, HbA1c, FPG

V6: CBC, electrolytes, BUN, creatinine, Lipids (TG, TC, HDL-c), ALT, AST, bilirubin (total and direct), HbA1c, FPG

V7: CBC, electrolytes, BUN, creatinine, HbA1c, FPG

V8-V14 and ET: CBC, electrolytes, BUN, creatinine, Lipids (TG, TC, HDL-c), ALT, AST, bilirubin (total and direct), HbA1c, FPG

- Clean catch sample to be collected at each visit. If urine is dipstick positive for WBC or blood sample is to be sent for microscopic evaluation and culture. Urine pregnancy test and drug screen on screening (visit 1)
- Adverse events of special interest are specified to be:
 - Cardio- and cerebro- vascular events,
 - Genitourinary infections
 - Increase in creatinine from baseline by 0.5 mg/dL or more
 - Increase in ALT, AST or bilirubin to >3x ULRR

Confidential Page 58 of 61

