**Table 1: Schedule of Events** 

		ening un-in		Treati	nent w	eeks 1	to 24			Treati	nent w	eeks 25	to 96		Follow Up 
Visit Number	1	2	3	4	5	6	7	8	9	10	11	12	13	14	15
Time to Randomization Visit (weeks) 	-5	-2	0	2	6	12	18	24	36	48	60	72	84	96	1 wk f/u
Informed Consent	X														
Screening for I/E criteria	X	X	X												
Medical History	X														
Diet & exercise counseling 		X				X		X		X		X			
Diary & glucometer record review			X	X	X	X	X	X	X	X	X	X	X	X	X
Discontinue anti-diabetic medication		X													
Randomization			X												
Physical exam 	X					X		X		X		X		X	X
Vital signs	X	X	X	X	X	X	X	X	X	X	X	X	X	X	X
ECG	X		X					X			X			X	X
Dispense study medication		X	X		X	X	X	X	X	X	X	X	X		
Blood draw for clinical lab test 	X		X	X	X	X	X	X	X	X	X	X	X	X	X
Urinalysis 	X		X	X	X	X	X	X	X	X	X	X	X	X	X
NMP22 testing 	X		X					X		X		X		X	
$AE^7$			X	X	X	X	X	X	X	X	X	X	X	X	X
Con Med		_	X	X	X	X	X	X	X	X	X	X	X	X	X

Screening period may last up to 21 days (V1 to V2), Run-in period is to be 14±3 days (V2 to V3), V3 to V8 window is ±3 days, all other visit windows are the nominal duration from randomization ± 6 days.

Glucose meter will be dispensed at visit 2. Training on using glucometer and recording hyper- or hypoglycemia will be conducted on visit 2.

- A complete physical examination will be performed by the investigator at screening and at the termination visit. An abbreviated physical examination will include body weight and general assessment of the skin, heart, lungs and abdomen. Abbreviated physical examinations will be performed by the investigator at all other time points, unless clinically indicated.
-  Blood sample for these lab tests at the designated visit are listed as following. Fasting state must be confirmed.
  - V1: CBC, electrolytes, BUN, creatinine, Lipids (TG, TC, HDL-C), ALT, AST, bilirubin (total and direct), PT, HbA1c, FPG, TSH, Hepatitis Screen (HBsAg, HBcAb, HCV), serum pregnancy for women of childbearing potential
  - V3: CBC, electrolytes, BUN, creatinine, Lipids (TG, TC, HDL-c), ALT, AST, bilirubin (total and direct), HbA1c, FPG
  - V4: CBC, electrolytes, BUN, creatinine, HbA1c, FPG
  - V5: CBC, electrolytes, BUN, creatinine, HbA1c, FPG
  - V6: CBC, electrolytes, BUN, creatinine, Lipids (TG, TC, HDL-c), ALT, AST, bilirubin (total and direct), HbA1c, FPG
  - V7: CBC, electrolytes, BUN, creatinine, HbA1c, FPG

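### The only scheduled pregnancy test is at Visit 1, 11 to 38 days before the first double-blind dose, and nothing repeats it on Day 1

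*Protocol*

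**What the plan says.** Protocol 4.3, exclusion 11, rules out pregnant women, and Protocol 6.9.4 says that a woman found to be pregnant before dosing may not be enrolled or given study drug. Eligibility is checked again at the point of randomization. Section 3.1 states: "After the run-in period, approximately 300 subjects will complete the baseline assessment on day 1 after overnight fasting to confirm their eligibility". The Visit 3 list in 7.2.1 includes "Confirm eligibility".

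The scheduled testing is as follows.

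- **Protocol 7.1.1 (Visit 1):** "Urine pregnancy test (only for females who are not postmenopausal".
- **Protocol Appendix 1, footnote 3:** "Urine pregnancy test and drug screen on screening (visit 1".
- **Protocol 6.7.1:** urine hCG is in the test list, with timing left to Appendix 1.
- **Protocol 7.2.1 (Visit 3):** no pregnancy test.
- **SAP Table 1, footnote 4, Visit 1:** "serum pregnancy for women of childbearing potential".
- **SAP Table 1, footnote 4, Visit 3:** "V3: CBC, electrolytes, BUN, creatinine, Lipids (TG, TC, HDL-c), ALT, AST, bilirubin (total and direct), HbA1c, FPG". No pregnancy test is listed.

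Both documents give the same interval. Protocol section 7 has "Screening period may last up to 21 days (Visit 1 to Visit 2), Run-in period is to be 14 ± 3 days" and SAP Table 1 has "Screening period may last up to 21 days (V1 to V2), Run-in period is to be 14±3 days (V2 to V3".

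Outside this schedule, Protocol 6.9.4 requires two contraceptive precautions for sexually active women of childbearing potential, with exceptions for sterility and abstinence. It asks women to contact the investigator if they think they may be pregnant. If pregnancy is suspected before dosing, drug is withheld until blood and urine tests are back.

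**The concern.** Re-confirming eligibility does not by itself mean re-testing every criterion. Pregnancy differs from most exclusions because it can begin, or first become detectable, between Visit 1 and Day 1. A negative screening result cannot rule out a conception that came later or was too early to show.

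The contraception and reporting rules lower the risk, but they cannot find a case that nobody suspects. Such a woman could be randomised and dosed against exclusion 11. No later visit schedules a test either, so Day 1 is the last point at which exposure to active drug can be prevented rather than stopped.

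What is at stake is participant protection. This is a gap in detection, not a contradiction between parts of the plan. It does not touch the primary endpoint, the power, the error rate or expedited reporting of pregnancies.

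**Working it through.** **Check on the interval inputs.** The plan states a maximum duration of 102 weeks (Protocol 3.3). Screening 3 + run-in 2 + treatment 96 + follow-up 1 = 102 weeks, which matches. Nominal Visit 1 to Visit 3 is 21 + 14 = 35 days = 5 weeks, which matches the week -5 column in Appendix 1.

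**Age of the Visit 1 result at the first double-blind dose.**

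- Visit 1 to Visit 2: 0 to 21 days. A maximum is stated but no minimum.
- Visit 2 to Visit 3: 14 ± 3 = 11 to 17 days.
- Minimum: 0 + 11 = 11 days. This needs Visits 1 and 2 on the same day, so real gaps will usually be longer.
- Maximum: 21 + 17 = 38 days.
- Nominal: 35 days, or 32 to 38 with the run-in window.
- If a subject who had not fasted returns up to 7 days later and dosing waits for that visit, 38 + 7 = 45 days.

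**Expected number of pregnancies that a Visit 3 test would find.**

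E = W × r × (d / 30) × (1 − s)

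Here W is the number of women who are not postmenopausal, r the conception rate per month, d the interval in days, and s the share already caught through suspicion before Day 1. The documents give none of W, r or s. The assumed ranges are W = 30 to 60, r = 0.1 to 1% per month and s = 0 to 0.8. The interval d = 11 to 38 days comes from the step above.

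| s | Low end | High end |
|---|---|---|
| 0 | 30 × 0.001 × 11/30 = 0.011 | 60 × 0.01 × 38/30 = 0.76 |
| 0.5 | 0.011 × 0.5 = 0.0055 | 0.76 × 0.5 = 0.38 |
| 0.8 | 0.011 × 0.2 = 0.0022 | 0.76 × 0.2 = 0.152 |

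A mid-range choice of W = 45, r = 0.3%, d = 35 and s = 0.5 gives 45 × 0.003 × 35/30 × 0.5 = 0.079.

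The formula counts every conception in the interval as detectable at Visit 3, which is generous. It leaves out conceptions just before Visit 1 that were too early to show then, which acts in the other direction.

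**The case against.** **The supplied protocol may be out of date on this item.** It is the original of 02 February 2011, while the SAP's Table 14.1-1.3 shell names versions of 11 April, 18 August and 12 September 2011. Exclusion numbering there runs to EX16 for April and EX19 for the later two. The Visit 1 test also changed from urine in the protocol to serum in SAP Table 1, so pregnancy testing was probably revised. This stands as a reason to check first. It does not remove the point: the SAP is dated 22 November 2011, after all three versions, and its revised schedule still shows the test at Visit 1 only. A SAP does not govern clinic procedures, but if a later protocol does have a Visit 3 test, the SAP table is wrong.

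**Safeguards already exist.** Contraception, counselling, two eligibility checks after screening and suspicion-triggered testing are all in place. They reduce the risk, but none detects an unsuspected pregnancy, and the protocol itself acknowledges that a single contraceptive method can fail.

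**The risk is small and its size is assumed.** This stands. The 0.76 figure takes every unfavourable input at once, including a monthly rate equal to about 11% a year despite the two-method rule. The documents also report no effect on in utero development in rats and rabbits (Protocol 1.1.1).

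**The fix covers little of the time at risk.** At most 38 of 38 + 672 = 710 days, about 5%, are covered, and the plan relies on suspicion for the other 96 weeks. The arithmetic is right. Day 1 still differs from later visits because a positive result there prevents exposure altogether.

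**Conclusion.** The concern holds. In the supplied protocol and in SAP Table 1, the only scheduled pregnancy test is 11 to 38 days old at the first double-blind dose, and no scheduled step on Day 1 would detect an unsuspected pregnancy. The interval follows directly from the stated windows.

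The expected yield of a Day 1 test is below one case: 0.002 to 0.76 across the assumed ranges, and about 0.08 at mid-range. Those figures rest on assumed numbers of women, conception rates and suspicion shares, and only their order of magnitude should be relied on. No analysis or conclusion of the trial changes. The change is worth making because it protects participants at very little cost. Confidence is medium, because the later protocol versions were not available.

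**What to change.** 1. Check whether the protocol versions of 11 April, 18 August or 12 September 2011 already contain a Visit 3 pregnancy test. If one does, only SAP Table 1 needs correcting.
2. If none does, add an on-site urine hCG test at Visit 3 for women who are not postmenopausal, in Protocol 7.2.1, Appendix 1 footnote 3 and SAP Table 1.
3. State that the sample is collected and the result read before randomization and dispensing. This needs saying because 7.2.1 lists urinalysis after both, and SAP Table 1 sends the visit urine to the central laboratory, so a result could otherwise arrive after dosing.

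The cost is one line in each of three places and about 30 to 60 on-site tests under the assumption above. Urine is already collected at Visit 3, SAP Table 1 already has an on-site dipstick there, and urine hCG is already in the 6.7.1 list. No extra visit or blood draw is needed. The limitation is that a very early pregnancy can still be missed.
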